### **9.2 Primary Endpoint**

The primary efficacy endpoint is defined as freedom from recurrent VT, cardiovascular rehospitalization, and all-cause mortality through a period of 2 years after the procedure (ablation) or randomization (standard medical therapy). Recurrent VT is defined as any appropriate ICD therapy (shock or ATP) or documented sustained monomorphic VT >30 seconds. Cardiovascular rehospitalization is defined as a hospital admission after the randomized procedure for heart failure, procedure-associated complication, or arrhythmia-related causes during the follow-up period.

Prespecified secondary endpoints include each of the individual components of the primary endpoint. Comparison of the ablation-only registry with the randomized patients will serve as an additional secondary outcome measure.

Prespecified subgroup analysis will be performed for patients with RV cardiomyopathy.

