#### **3.5.1 Randomization**

Subjects who meet inclusion/exclusion criteria will be entered into the randomized trial. Randomization will be 1:1 between control group and ablation group. Those randomized to the control group will receive ICD therapy and routine drug therapy (including antiarrhythmic drugs as indicated). Subjects randomized to the ablation group will receive ablation therapy plus ICD for ventricular tachycardia. Patients that refuse ICD therapy and undergo ablation only will be enrolled in a prospective registry. All primary statistical analyses will be performed on an intent-to-treat basis.

Central randomization is conducted by the coordinating site. Prior to 10/12/16, the participating sites performed randomization using a table (block size of 4) provided by the coordinating site. After additional in-house statistical review of the protocol, electronic randomization from the coordinating site was advised. Central electronic randomization commenced on 10/12/2016. 25 patients were enrolled using the original randomization table schema. The remaining patients were randomized using electronic randomization.

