### 3.6 Study Population

#### 3.6.1 Randomized Subjects

The **Intent to Treat (ITT)** population includes all randomized subjects. These subjects can be included in the randomized trial if they meet all other entry criteria.

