### **4.2 Subject Screening and Informed Consent**

All patients who are being considered for enrollment into the clinical trial must be screened by the site investigator or a member of the designated study staff for study eligibility.

Patients must sign the informed consent form prior to randomization or collection of any study data. Once randomized, they will be considered enrolled in the study. The Investigator, Co-Investigator or Research Coordinator and if necessary, any witnesses should sign and date the consent as well. Consented subjects who do not satisfy entry criteria are screen failures and will not be randomized.

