### **9.3 Primary Endpoint Analysis**

The primary endpoint analysis will be a time to event analysis and account for censored observations for all randomized subjects. Intention to treat analysis will be used for this endpoint; the analysis will be “analyzed as randomized” regardless of the actual treatment patients receive during the follow-up period. Kaplan-Meier (1958) estimates of the primary endpoint and overall survival will be generated along with 95% confidence intervals for the median time to event or death (Brookmeyer and Crowley, 1982).(8,9) Log-rank test will be used to compare the hazard functions between the two groups. Cox (1972) regression models will be fit to assess and adjust for baseline covariates.(10) The median time to VT recurrence as well as the 95% confidence intervals will be reported for both groups. The event free survival probability as well as the 95% confidence intervals at the 24-month follow-up for both groups will be presented. Adverse events will be tabulated by type and level of severity and compared between groups using chi-square or Fisher exact tests.

Secondary analyses comparing outcomes in the ICD+ablation and ICD arms vs. the registry patients (ablation only) will be performed in a similar manner to those described above.

Interim analyses will be generated by the coordinating center annually. A Peto-Haybittle efficacy monitoring boundary will be used: if the p-value for the difference between groups is <0.001, early stopping of the trial will be considered. Using this monitoring bound, the p-value for statistical significance at the final analysis will remain at the nominal 0.05 level.

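### The 2-year primary endpoint starts at the procedure in the ablation arm but at randomization in control, which cannot be squared with an intention-to-treat analysis of all randomized patients

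*Combined protocol and SAP*

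**What the plan says.** - **Time origin.** Sections 3.2 and 9.2 use the same words: the primary endpoint is followed "through a period of 2 years after the procedure (ablation) or randomization (standard medical therapy"). The ablation clock starts at the procedure, the control clock at randomization.
- **Rehospitalization.** This component has its own start: "a hospital admission after the randomized procedure for heart failure, procedure-associated complication, or arrhythmia-related causes during the follow-up period". The randomized procedure is not defined for control. It could mean the ICD implant, which the section 4.7 table lists under Procedure, or randomization itself.
- **Analysis set.** Section 3.5.1: "All primary statistical analyses will be performed on an intent-to-treat basis". Section 3.6.1 says the ITT "population includes all randomized subjects". Section 9.3: "The primary endpoint analysis will be a time to event analysis and account for censored observations for all randomized subjects", with patients kept in their assigned arm whatever treatment they receive.
- **Enrollment.** Section 4.2: "Once randomized, they will be considered enrolled in the study".

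No section gives a maximum time from randomization to ablation, a start date for a patient never ablated, or a rule for events between randomization and ablation. The 90-day window in section 3.4.1 concerns ICD implant relative to enrollment, not ablation. Section 3.6.3 censors discontinued patients but does not say where their time starts.

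**The concern.** A log-rank comparison of all randomized patients needs a start date for each of them, set in the same way in both arms. Here the start in one arm depends on something that happens after randomization. This causes three problems.

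1. A patient randomized to ablation who dies first, withdraws or never has the procedure has no defined time zero, yet must be in the analysis.
2. Events during the wait fall before the ablation clock starts, while control events over the same interval count.
3. The arms are compared over different stretches of time since randomization. If risk is highest soon after enrollment, the ablation arm is observed only from a later, quieter point.

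Without a rule, the analyst must decide after the fact which early events and patients count. That choice reaches the primary log-rank test, the Kaplan-Meier curves, the 24-month event-free estimate and the annual interim looks.

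Only the interval from randomization to procedure is affected. Events after the procedure, including complications leading to admission, do count against ablation.

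**Working it through.** **Inputs from the plan.** 60 patients per arm (section 1); 50% control events at 2 years, a 50% reduction (hence 25% with ablation), 80% power and two-sided alpha 0.05 (section 9.1); log-rank test (section 9.3).

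**The plan's own figure.** For two proportions, 0.50 against 0.25 with 60 per arm, power = Φ{[0.25√60 − 1.96√(2 × 0.375 × 0.625)] / √(0.25 + 0.1875)} = 81.6%. By Freedman's formula with hazard ratio ln 0.75 / ln 0.50 = 0.415, 46 events are needed, and 46 / 0.375 = 123 patients. The stated 120 and 80% are therefore reproduced. The formulas have no time-zero input, so the issue does not make 120 wrong. It concerns the validity of the test and the meaning of the effect.

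**Assumptions, because the documents are silent.** A fixed wait d for every ablation patient of 2 weeks, 1 month or 3 months. Control cumulative hazard L(t) = ln 2 × (t/24)^k, t in months, which gives 50% events at 24 months for any k. k = 1 is constant hazard; k = 0.75 and 0.5 are falling hazards.

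**Step 1: share of patients with a first event before the procedure**, 1 − exp(−L(d)).

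| k | 2 weeks | 1 month | 3 months |
|---|---|---|---|
| 1 | 1.3% | 2.8% | 8.3% |
| 0.75 | 3.5% | 6.2% | 13.6% |
| 0.5 | 9.2% | 13.2% | 21.7% |

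Example, k = 1, d = 3: L = 0.693 × 3/24 = 0.0866, and 1 − exp(−0.0866) = 8.3%, or 5 of 60. At k = 0.5 and 3 months it is 13 of 60, leaving about 47.

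**Step 2: 2-year risk shown by the ablation arm if ablation does nothing**, 1 − exp(−[L(24+d) − L(d)]), against 0.500 in control.

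| k | 2 weeks | 1 month | 3 months |
|---|---|---|---|
| 1 | 0.500 | 0.500 | 0.500 |
| 0.75 | 0.487 | 0.478 | 0.457 |
| 0.5 | 0.453 | 0.432 | 0.387 |

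**Step 3: two-sided type I error of the log-rank test.** Simulated with 60 randomized per arm, censoring at 24 months, ablation patients with a pre-procedure event removed, and 20,000 runs.

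| k | 2 weeks | 1 month | 3 months |
|---|---|---|---|
| 1 | 0.054 | 0.047 | 0.053 |
| 0.75 | 0.052 | 0.061 | 0.082 |
| 0.5 | 0.094 | 0.143 | 0.273 |

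At k = 0.5 nearly all rejections favour ablation. Repeat simulations agree within simulation error. With both arms timed from randomization, the error stays at about 0.05 throughout.

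**Step 4: the opposite direction.** Suppose control patients wait for an ICD and events go undetected meanwhile. As an extreme bound under constant hazard, if every control event in the first w months were missed, control would show 1 − exp(−[L(24) − L(w)]) = 48.5% (w = 1) or 45.5% (w = 3), against 50% in ablation. This would work against ablation.

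**The case against.** **The sentence may not exclude early events.** It says how long freedom from events must last, and a patient who dies before ablation is not free of death two years after it. Read with the all-randomized rule in section 9.3, one could count from randomization until 24 months after the procedure. Simulated with no true effect, that reading gives type I error of about 0.044 to 0.055 for every shape and wait above, so the inflation disappears. This shows that the bias depends on how the text is read. But the reading is strained, it does not fit the rehospitalization definition ("Cardiovascular rehospitalization is defined as a hospital admission after the randomized procedure"), and a never-ablated patient still has no end date.

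**Intention to treat fixes the arm and the analysis set, not the clock.** True, but a time-to-event analysis of all randomized patients still needs a start date for each, and some have none.

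**The larger error rates rest on assumptions.** This stands. Section 9.1 gives only an annual rate of about 10% each for rehospitalization and death. That is closer to a constant hazard, and it says nothing about the shape for VT. The 0.27 figure needs both a steep early hazard and a 3-month wait for everyone. The section 4.7 table puts ICD implant and ablation in one Procedure column ahead of the 3-month visit, so shorter waits may be more typical. At 2 weeks and shape 0.75 the inflation is negligible.

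**The reverse case is only a bound.** Also true: deaths and admissions need no ICD to be detected.

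**Conclusion.** The concern holds, and the primary endpoint definition must be corrected. Its start rule cannot be applied to every randomized patient, and nothing elsewhere in the plan supplies the missing rule. That conclusion rests on the text alone.

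The numerical effect is conditional. Type I error is not inflated if the hazard is constant. It is about 0.05 to 0.08 at Weibull shape 0.75 and 0.09 to 0.27 at shape 0.5, for waits of 2 weeks to 3 months with pre-procedure events removed. Undetected early events in control could push the bias the other way. Since waits, hazard shape and detection are all assumed, the actual size and direction are unknown. The planned sample size of 120 is not called into question by this point.

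**What to change.** In sections 3.2, 9.2 and 9.3:

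- Start every component of the primary endpoint, and the 24-month event-free estimate, at the date of randomization in both arms.
- Count all qualifying events from that date for all randomized patients, including those never ablated.
- Define rehospitalization as a qualifying admission after randomization, excluding the planned index admission for the assigned ablation or ICD implant.
- Report the interval from randomization to procedure by arm.
- Keep the procedure-based clock only as a labelled sensitivity analysis.

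**Cost.** This is a wording change plus a check that a randomization date is held for every patient. The CRF components in section 4.8 do not name one, although that list gives form titles rather than data fields. The 25 patients randomized from site tables before central electronic randomization (section 3.5.1) deserve particular attention.

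The result may be less favourable to ablation, and this should be disclosed. If ablation acts only after the procedure (hazard ratio 0.415, 60 per arm), simulated power with the randomization clock is:

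| k | no wait | 2 weeks | 1 month | 3 months |
|---|---|---|---|---|
| 1 | 83% | 80% | 77% | 63% |
| 0.75 | 83% | 75% | 69% | 51% |
| 0.5 | 82% | 62% | 51% | 31% |

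Sections 1 and 3.6.2 state that no statistical review or analysis had been done as of April 28, 2020. On that account the clock could be settled before results are known.

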#### **3.2 Study endpoints**

The primary efficacy endpoint is defined as freedom from recurrent VT, cardiovascular rehospitalization, and all-cause mortality through a period of 2 years after the procedure (ablation) or randomization (standard medical therapy). Recurrent VT is defined as any appropriate ICD therapy (shock or ATP) or documented sustained monomorphic VT >30 seconds. Cardiovascular rehospitalization is defined as a hospital admission after the randomized procedure for heart failure, procedure-associated complication, or arrhythmia-related causes during the follow-up period.

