### 3.4.1 Inclusion Criteria

- Patient is receiving a new ICD or CRT-D implant that has study required programming capabilities and is appropriate for remote monitoring. Patient who has received the ICD / CRT-D within 90 days of enrollment can also be enrolled.
- Patient who has a high risk of ICD shock as shown by documented Monomorphic VT (MMVT) by one or more of the following:
  - Spontaneous MMVT
  - Inducible MMVT during EP Study,
  - Inducible MMVT during NIPS Study

\*Inducible MMVT is defined as MMVT > 30 seconds or requiring electrical termination (ATP or cardioversion)

- Patient has EF < 50% or RV dysfunction
- Patient has a cardiomyopathy with structural heart disease of any cause
- 18 years of age or older
- Patient has been informed of the nature of the study and has agreed to its provisions and provided written informed consent approved by the Institutional Review Board.

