#### **4.5.3 Procedural Endpoints**

Programmed stimulation is required before the ablation procedure with two cycle lengths (600ms and 400ms up to triple extrastimuli down to VERP or 200 ms). This may be performed through the implanted ICD (NIPS). A VT is considered clinical if there is a morphologic match by 12-lead ECG or intracardiac EGM or has a similar tachycardia cycle length. Left ventricular stimulation within scar should be performed if the patient is noninducible with RV stimulation. Substrate-based ablation strategy targeting abnormal regions of slow conduction can be performed in the event of noninducibility.

The acute procedural endpoint is noninducibility of the targeted clinical VT and elimination of abnormal electrograms within scar. Programmed stimulation will be performed in the same fashion as prior to ablation. Complete noninducibility is encouraged but not required.

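### The primary endpoint counts planned as well as unplanned arrhythmia admissions, so an elective crossover ablation makes an event-free control patient a primary failure

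*Combined protocol and SAP*

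**What the plan says.** Sections 3.2 and 9.2 define the primary composite in the same way: recurrent VT, cardiovascular rehospitalization or death from any cause, over 2 years. For the admission component: "Cardiovascular rehospitalization is defined as a hospital admission after the randomized procedure for heart failure, procedure-associated complication, or arrhythmia-related causes". Neither section uses the word unplanned or an equivalent, and no other section excludes elective admissions.

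For the arrhythmia component: "Recurrent VT is defined as any appropriate ICD therapy (shock or ATP) or documented sustained monomorphic VT >30 seconds". *Appropriate* is not defined, and spontaneous onset is not required. The eligibility criteria in section 3.4.1 do separate spontaneous from inducible VT.

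Section 9.3 specifies a time-to-event analysis by randomized arm, "regardless of the actual treatment patients receive during the follow-up period". No rule says whether an admission to receive the other arm's treatment is itself an event. Under section 9.2 the 2-year period runs from the procedure in the ablation arm and from randomization in the control arm.

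No blinding, sham procedure or endpoint committee is described. Sections 4.9 and 10 leave monitoring to each site.

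**The concern.** An elective admission is a management decision, not a failure of treatment. Consider a control patient who has had no VT, no heart failure admission and no ICD therapy, and who is then booked for the ablation withheld at randomization. That admission is arrhythmia-related, so the patient fails on the day of admission. An ablation-arm patient has already had the first ablation by time zero and cannot fail by that route.

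The staff who decide whether to book the admission appear to know the allocation, and the same sites report the event. If such admissions are more frequent among controls, they add control failures that ablation did not prevent, and the primary comparison shifts toward ablation. If they are equally frequent in both arms, they dilute the contrast and cost power.

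**Working it through.** **Inputs from the documents.** 120 patients randomized 1:1, so 60 per arm (sections 1 and 3.5.1). Control event rate 50% at 2 years, a 50% reduction with ablation (so 25%), two-sided alpha 0.05 and 80% power (section 9.1).

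**Assumed input.** q is the share of otherwise event-free patients who fail only through an elective admission. The documents give no such rate, so I use 5%, 10% and 20%. Among controls, 50% of 60 leaves 30 event-free patients, so these values correspond to 1.5, 3 and 6 extra failures.

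**Formulas.** Observed rate = p + (1 − p)q. The planned log-rank test is approximated by a comparison of two proportions. With d = pC − pA and p̄ the mean of the two rates:

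- SE0 = √[2p̄(1 − p̄)/60]
- SE1 = √{[pC(1 − pC) + pA(1 − pA)]/60}
- Chance of a significant result favoring ablation = Φ[(d − 1.96·SE0)/SE1]

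**The plan's own figure.** With 50% against 25%: d = 0.25, SE0 = 0.0884, SE1 = 0.0854, so Φ[(0.25 − 0.1733)/0.0854] = Φ(0.90) = 81.6%. The stated 80% power with 120 patients is reproduced. The gap in the definition does not make that figure wrong.

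**No true effect, 50% rate in both arms.** Example with q = 10% in controls only: pC = 0.50 + 0.50 × 0.10 = 0.55 and pA = 0.50, so SE0 = 0.0912 and SE1 = 0.0911. Then Φ[(0.05 − 0.1787)/0.0911] = Φ(−1.41) = 7.9%. Exact binomial results are in parentheses.

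| q in controls | Control rate | Ablation arm q = 0 | Ablation arm half of q | Ablation arm same q |
|---|---|---|---|---|
| 0% | 50% | 2.5% (2.7%) | 2.5% (2.7%) | 2.5% (2.7%) |
| 5% | 52.5% | 4.6% (5.0%) | 3.4% (3.7%) | 2.5% (2.7%) |
| 10% | 55% | 7.9% (8.5%) | 4.6% (4.9%) | 2.5% (2.7%) |
| 20% | 60% | 19.4% (20.4%) | 8.0% (8.3%) | 2.5% (2.6%) |

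**Dependence on the base rate.** With extra events in controls only and a true rate of 25% in both arms, the three values of q give 6.7%, 14.6% and 41.7%. The 50% rate is used for the main illustration because it is the plan's own control rate.

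**Planned effect present, same q in both arms.** The observed rates become 52.5% against 28.75%, 55% against 32.5%, and 60% against 40%. Power falls from 81.6% to 76%, 71% and 59%.

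**The case against.** Three arguments against the concern have force.

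- **Direction.** A reader might infer that such events fall mainly on controls. The documents do not show this. Repeat ablations would count in the ablation arm, and so would complication admissions, which the same sentence makes events. Section 4.6.2 applies the same drug-continuation rule to both arms and leaves drugs after ablation to the physician, so drug-related admissions are not a control-only route. The phrase in section 9.3 about actual treatment is ordinary intention-to-treat wording and does not show that crossover is expected. What remains is that a first elective ablation after time zero is possible only in controls.
- **First event.** If time to first event is analyzed, as is usual for a composite, an elective ablation after VT, ICD therapy or a heart failure admission adds no failure. Only crossovers with no earlier event matter. The illustration counts only those, but their number is unknown.
- **Judgment.** Planned or unplanned status would be assessed by the same sites, so the fix moves some discretion and does not remove it. Recording the reason and running a sensitivity analysis limit this.

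A reader might also infer that therapies delivered during device testing count as failures. The text does not say so. *Appropriate* can be read to exclude them, and sections 4.7 to 4.7.2 list device interrogation in follow-up, with no induction test. The protocol-required stimulation is in section 4.5, which covers the ablation arm only: "Programmed stimulation will be performed in the same fashion as prior to ablation". Section 4.5.4 has ICD therapies switched off during mapping and ablation. The narrower point stands: the limb for VT over 30 seconds does not exclude an induced episode.

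Finally, the trial is not called open-label. That is inferred from the absence of any described blinding or sham.

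**Conclusion.** The concern holds for the admission component. As written, an elective arrhythmia admission is a primary event, and a control patient without an earlier event who is admitted for ablation is scored as a failure. The likely direction favors ablation, but the net direction is not established.

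The size is unknown. At the plan's 50% rate, the chance of a false result favoring ablation rises from about 2.5% to about 5%, 8% or 20% if 5%, 10% or 20% of event-free controls are affected and no ablation patients are. It is about 4%, 5% or 8% if the ablation arm has half as many such events. With equal rates there is no bias, and the cost is power. These figures rest on the assumed q and on the two-proportion approximation.

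The VT component is a secondary matter: the status of induced episodes is ambiguous, but the text does not establish that they count. The endpoint definition should be corrected. The sample size calculation does not need to change on this account.

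**What to change.** In sections 3.2 and 9.2:

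- Limit the admission component to unplanned admissions, and limit the VT component to spontaneous VT and ICD therapy for spontaneous VT or VF.
- Add one sentence that applies to both arms: elective admissions without a complication, including crossover and repeat ablation, and VT induced at EP study, NIPS or device testing are not endpoint events. A crossover ablation then counts only through a spontaneous arrhythmia or unplanned admission that led to it, or through a complication.
- Record planned or unplanned status, with the reason, on the existing case report forms.
- Prespecify a sensitivity analysis that counts elective ablation admissions as events, so that readers can see whether the result depends on the rule.

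The rule should be set before anyone reviews outcomes by arm; the protocol states that no statistical review had been done as of 28 April 2020.

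The cost is a few words in the definition, one exclusion sentence, one added form item and one extra analysis. No treatment or visit changes. There will be slightly fewer events, and event-free crossovers will stay in follow-up as treated controls, which dilutes the contrast somewhat.

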## 2.2 Study Purpose

The purpose of this study is to demonstrate that scar-based VT ablation in subjects who are clinically indicated for new ICD or CRT-D implantation and are at high risk of ICD shock with spontaneous monomorphic VT or inducible monomorphic VT during EP or NIPS study results in a superior clinical outcome compared to ICD with standard medical therapy. Additionally, the registry arm which will enroll patients that refuse ICD will assess the efficacy of catheter ablation in the absence of background ICD therapy.

Additionally, secondary goals of this study include:

- 1) Increasing SCD awareness in Asia and improving clinical follow-up of patients at risk.
- 2) Assessing whether SCD is less prevalent in Asia than US and Europe and prospectively determine the relative magnitude of benefit of both ICD and ablation.
- 3) Determining the composition and etiology of patients referred for ICD and ablation in Asia. Patients with ischemic cardiomyopathy represent a

disproportionately small proportion of patients referred for VT ablation, despite a high prevalence of coronary artery disease and myocardial infarction. Biological and cultural differences in scar patterns may account for variations in arrhythmogenicity

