#### **4.8 Data Collection and Reporting**

All required data, including subject's medical history for this trial are collected on standardized Case Report Forms (CRFs). CRFs were designed to balance the need for comprehensive data collection and to ease the process of data acquisition at the clinical center. The study coordinating site will provide each site with template CRFs to assist with data collection.

Components of the CRF:

- Subject selection criteria
- Medical History
- Medications
- Preoperative baseline subject demographics
- Ablation Procedure forms
- Device Operation Form
- ICD implantation information
- Pre-discharge hospital summary (including post-procedural complications, etc.)
- Assessment data at follow-up
- Adverse event/ Serious adverse event
- Unanticipated Adverse Device Effect
- Report of Death
- Subject Withdrawal
- Protocol Deviations

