#### 5.1.2 Serious Adverse Events Definition (SAE)

A serious adverse event is defined as an adverse event that results in:

- A. Death
- B. Serious deterioration in the health of the subject that:
  - 1) Results in a life-threatening illness or injury;
  - 2) Results in permanent impairment of a body structure or a body function;
  - 3) Requires inpatient hospitalization > 24 hours or prolongation of existing hospitalization;
  - 4) Results in medical or surgical intervention to prevent permanent impairment to body structure or a body function.

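### Procedure complications enter the primary composite only through a new admission, so non-fatal, non-VT complications that merely prolong the index stay are not counted, which tends to favour ablation

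*Combined protocol and SAP*

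**What the plan says.** The primary composite in 9.2 (same text in 3.2) is recurrent VT, cardiovascular rehospitalization and death from any cause over 2 years. The rehospitalization component reads: "Cardiovascular rehospitalization is defined as a hospital admission after the randomized procedure for heart failure, procedure-associated complication", with arrhythmia as the remaining qualifying cause. Prolongation of a stay already in progress is not mentioned.

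No safety endpoint is named. On secondary endpoints, 9.2 says: "Prespecified secondary endpoints include each of the individual components of the primary endpoint". It adds only the comparison with the ablation-only registry.

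The serious adverse event definition in 5.1.2 is wider than the endpoint. One of its criteria is: "Requires inpatient hospitalization > 24 hours or prolongation of existing hospitalization". Adverse events are assessed before discharge (4.6.1), and the case report form includes a pre-discharge summary covering complications of the procedure (4.8). Section 9.3 then says: "Adverse events will be tabulated by type and level of severity and compared between groups using chi-square or Fisher exact tests".

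Under 3.5.1 both arms receive an ICD and only one is assigned ablation. Section 2.2 states the aim as showing that ablation "results in a superior clinical outcome compared to ICD with standard medical therapy".

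**The concern.** The plan chose to let procedure complications count in the composite, and then tied them to a new admission. Cardiac perforation with tamponade, coronary occlusion, cardiogenic shock and vascular access injury are all listed as risks in 7.1, and each can arise during the procedure or before discharge. When that happens the current stay lengthens and no new admission need follow.

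The result is an ordering that is hard to defend. A groin haematoma readmitted on day 5 is a primary event. A tamponade repaired surgically, with three more weeks in the same stay, is not. The component-wise secondary endpoint for rehospitalization inherits the same gap. Because ablation is given in one arm only, the omitted events fall mainly in that arm, and the composite would look somewhat better for ablation than the patients' course warrants.

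**Working it through.** **Which index-stay events count under 9.2**

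| Event before discharge | Counted? | Route |
|---|---|---|
| Death | Yes | All-cause mortality |
| Sustained monomorphic VT or appropriate ICD therapy after the procedure | Yes | Recurrent VT |
| Non-fatal, non-VT complication, later readmitted for it | Yes, at readmission | Rehospitalization |
| Non-fatal, non-VT complication that only prolongs the stay | No | None |

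The gap is the last row. The same event is an SAE under 5.1.2.

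**The plan's own figure.** Inputs from 3.5 and 9.1: 50% control events at 2 years, a 50% reduction (read as 25% with ablation), 60 per arm, two-sided alpha 0.05. For two proportions with pooled variance under the null:

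power = Φ{ [ |p1 − p2|√n − 1.96√(2p̄(1 − p̄)) ] / √(p1(1 − p1) + p2(1 − p2)) }

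= Φ{ [0.25 × √60 − 1.96 × √0.46875] / √0.4375 } = Φ(0.899) = 81.6%.

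The stated 80% with 120 patients is reproduced. Expected events are 60 × 0.50 = 30 in control and 60 × 0.25 = 15 with ablation.

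**Size of the omission.** The documents give no complication rate. Let c be the assumed share of ablation patients with a stay-prolonging complication, independent of other composite events, with none in control. Some of these patients would have a composite event anyway, so the newly counted share is 0.75c and the ablation event rate becomes 0.25 + 0.75c.

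| c (assumed) | Patients affected | Newly counted events | Share of 15 | Ablation event rate | Relative reduction vs 50% |
|---|---|---|---|---|---|
| 0 | 0 | 0 | 0 | 25.0% | 50% |
| 5% | 3 | 60 × 0.0375 = 2.25 | 15% | 28.8% | 42.5% |
| 10% | 6 | 60 × 0.075 = 4.5 | 30% | 32.5% | 35% |

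With 60 per arm, the power formula gives 66.7% at c = 5% and 49.5% at c = 10%. The wider composite is therefore better placed as a sensitivity analysis than as the primary endpoint.

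**What the planned adverse event test can show.** With k events against 0 at 60 per arm, the two-sided Fisher p-value is 2 × C(60,k)/C(120,k):

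- 3 vs 0: p = 0.244
- 5 vs 0: p = 0.057
- 6 vs 0: p = 0.027

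Six complications in one pooled category would just reach 0.05. Split three and three over two types, each line gives p = 0.244. A comparison by type can therefore miss what a pooled one would show.

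**The case against.** The strongest reply is that these harms are already captured. They are assessed before discharge, recorded on the case report form, classed as serious if they prolong the stay, and compared between arms under 9.3. The composite is called an efficacy endpoint, and reporting safety separately beside it is a legitimate design. Both arms receive ICDs, so ICD complications in the index stay can go uncounted in control too. Naming a pooled comparison does not create power: even then 6 vs 0 is needed.

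Most of this stands. A reader might infer that nothing in the plan picks up these complications, or that every index-stay complication is left out. The documents do not support either: 9.3 compares adverse events between groups, and deaths and qualifying VT or ICD therapy do count. Nor does 7.1 give any timing, so one cannot say that most listed complications occur before discharge.

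Two things remain. The plan did not keep procedure complications out of its efficacy endpoint; it included them and then counted only those leading to readmission. And the adverse event comparison is broken down by type and severity, with no pooled procedure-related category and no stated window.

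**Conclusion.** The concern holds in a limited form. Non-fatal, non-VT complications that only prolong the index stay fall outside the composite, and the direction tends to favour ablation. They are visible only in a general adverse event comparison that is poorly suited to showing them.

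The size is not known. On an assumed rate of 5-10%, with independence and no matching control events, it is 2.25-4.5 ablation-arm events, or 15-30% of the 15 expected. One might take all 3-6 affected patients, or 20-40% of 15, as missed events; that overstates it, because about a quarter would reach the composite by another route. Matching ICD complications in control would narrow the difference between arms further.

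Nor does this show that the sample size is wrong: 120 is reproduced for the composite as defined. The point warrants a change to the plan, but not to the primary endpoint.

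**What to change.** Keep the primary composite, its test and N. Add to 9.2 and 9.3:

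1. **A prespecified sensitivity analysis of the composite**, applied identically in both arms and timed from randomization. It also counts, on its date, any SAE associated with the ablation or ICD procedure that meets the 5.1.2 criterion of a prolonged stay. Tying it to that recorded criterion matters because overnight observation is only recommended (4.6.1), so length of stay alone would reflect local discharge practice. Starting at randomization avoids the different time origins in 9.2 and the lack of a defined randomized procedure for control patients.
2. **One pooled between-arm comparison** of patients with any SAE related to the ablation or ICD procedure, index-stay events included, over one identical window from randomization in both arms. Report it beside the primary result as a difference with a confidence interval. A window ending a set time after each patient's last procedure would give the arms unequal exposure. The sponsor should fix a length that covers the ablation and early recovery, since the documents do not give the delay from randomization to procedure.

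State also how relation to the procedure is assigned, because section 5 asks about relation to the investigational system or device.

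The cost is some wording, one table and one further analysis. The pre-discharge summary and the AE/SAE forms already provide the data sources. The protocol states that no analysis had been done as of 28 April 2020; if that is still so, both can be prespecified. The downside is that the result may look slightly less favourable to ablation.
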